Participant Time:

Participants will be in the study for approximately 7 months, which will include the screening phase, a baseline phase, a 6-month intervention, a 3-month follow-up survey, and a 6-month follow-up survey.

Study Phase	Time
Initial Screening Survey (5 min)	5
Telephone Screening (30 min)	30
Baseline (65 min total) Scale/app set-up (15 min) Online survey (40 min) NDA acknowledgement (10 min)	65
Intervention Pilot (24 wks)/15 min/day Virtual workshops (24 wks)/30-60/day	1,080-1,800
Follow-up surveys: 3-month online survey (20 min) 6-month online survey (40 min)	60
Total	1,240-1,960 minutes (approx. 21-33 hrs)

Design, Procedures, Materials and Methods: [Describe the study design, including the sequence of study procedures. Experimental procedures should be clearly described and labeled as such. If the study uses control or experimental groups, or different treatment arms, clearly describe what participation will be like for each of the groups or study arms. Tip: describe procedures in the order conducted, where they will be conducted and how long they will take to complete. The IRB strongly suggests that investigators incorporate *flexibility* into the study design to accommodate anticipated events (i.e. explain how missed study appointments can be made up by participants). If this study offers treatment for the participants' condition, complete the Treatment Study Supplemental Form (IRB-1C) and attach it to this application for review. Use of a table is often helpful here.]

Study design: Participation starts with an initial survey, telephone screening, a 2nd survey to collect baseline assessment data, and acknowledgement of a Non-Disclosure Agreement with WW. Eligible participants will then complete an on-boarding process, which includes intervention platform set-up/invitation and scale set up. Participants will then complete a 6-month intervention, a 3-month survey, and a 6-month survey.

Recruitment

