The 6-month intervention includes the use of three components: WW's mobile app (Beta version of new program) weekly group virtual workshops, and a private Facebook group. The WW weight loss curriculum involves: self-monitoring of weight, dietary intake, and physical activity; making dietary changes; increasing physical activity; and learning behavioral strategies to manage these goals. Each week, participants will set goals and weigh in. Participants will be encouraged to use the app daily. WW staff will monitor all app use and Facebook use. Participants will be enrolled in cohorts. Once they confirm a day and time that they can attend the weekly virtual workshops, we will give them a start date and groups of participants approximately 20 or more will start at the same time.

WW Beta app – After downloading the WW Beta app by receiving a special link and access code, members will complete a personal assessment to determine which food plan to follow. They will then be guided on how to use the app and start their food plan.

Members can switch plans at any time. The app assigns each member a personalized SmartPoints budget that consists of daily SmartPoints. SmartPoints is the WW system used to take complex nutritional data and summarize it in a simple number that is easy for users to understand. The app will track daily their SmartPoint Budget and is how users keep track of their daily dietary intake and physical activity. The app also has other features (e.g., provides recipes tracking sleep with a synced fitness device).

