Virtual Workshops. Virtual workshops will be offered through Zoom. Links to Zoom virtual workshops will be accessed either through a link in the WW app, or in emails to study participants (sent by WW). If participants do not want to join by Zoom, they can call in. Participants will be asked to attend a virtual workshop weekly during the 6-month intervention. WW will offer several days and times for the participants. The workshops last between 30-60 minutes long and are led by a trained WW coach. The workshops are closed to only WW members within this study and will have no more than 20 participants per workshop. The virtual workshops are meant to provide group support to participants. They will discuss progress and setbacks, troubleshoot challenges, help with goal setting, and discuss and learn about various topics surrounding promoting a healthy lifestyle. These will not be recorded. Additionally, participants will have regular, short (~five minute) one-on-one check-ins with their coach in addition to the virtual group workshops.

Milestone Charms. To help retention rates in the study, WW will send participant's milestone charms for hitting a weight loss milestone during the intervention. These charms are small keychains that shows the milestone they have achieved. Participants will receive a weight loss charm if they hit these milestones of losing: 5lbs, 10lbs, 15lbs, 20lbs, 25lbs, 30lbs, 40lbs, 50lbs, 75lbs, 100lbs, 125lbs, 150lbs, 175lbs, and 200lbs. Milestone weight loss is reviewed each week by UConn staff. If a participant has hit a weight loss milestone, UConn sends the information over to WW via OneDrive (which participant, their address, and what milestone) and WW ships the charms out to

participants. This is set-up is the same as the scale shipping to participants. The participants can opt out of receiving charms at any point.

To avoid questions about the app's capabilities taking up a lot of time during the weekly workshops, WW will also hold additional workshops coined 'App Academy' to go over the app in more detail, walk through the functionalities and different features that the app has to offer and answer questions regarding the app. A WW coach leads this and it is optional. Participants can attend, none, one, or all App Academy times that they offer.

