Participant engagement data (i.e., WW app, Virtual Workshops, weight data) will be continuously collected by WW. Facebook engagement data will be collected through Grytics that study staff have access to through a secure login. The WW investigator will transfer these files via a UConn OneDrive folder which only [name] and [name] access. [name] or [name] will save the data to the UConn research drive and delete it from the OneDrive. WW will review by assigning a staff member to read and assess each interaction in the Facebook group on a regular basis. We will also assess for large weight changes to ensure only the participant is using the app. Any privacy-related problems will be brought to the attention of the PI immediately.

[Describe any anticipated inconveniences the participants may experience (such as: their time, abstention from food, etc.).]

Participants will be asked to dedicate up to 33 hours of their time over the course of 7 months to participate in this study.

Instances of threats or harassment in the Facebook group will be handled in the manner below:

Profanity & Vulgarity

- R-rated language
 - Remove all R-rated language used as a form of a personal attack, e.g. "You are a b****" or "F*** you". These specific words are not permitted at all times: "c***", "d***", "c**k", "b*** f***", "m****f*****".
- "Shit"
 - Permit content that contains the word "shit" and all of its variants, unless used in the form of a personal attack, e.g., "You don't know shit."
- "Ass", "Crap", "Bullcrap", "Hell", & "Damn"
 - Permit these words and their variants - kick ass, bad ass, pain in the ass, etc., unless used in the form of a personal attack, e.g., "I'm going to kick YOUR ass."
- Pornographic content & Sexually graphic or explicit language
 - Remove all pornographic content as well as sexually graphic or explicit language. Apply the standard of PG-13 TV. For example, it is ok for fans to say, "WW has helped me look sexier than ever!" However, it is not ok for fans to describe sexual acts in detail.
- Camouflaged spellings, e.g., "f*ck" or "p0rn"
 - Moderate words with transparently camouflaged spellings as you would their obvious stand-ins, e.g., "f*ck" is permitted, as long as it is NOT used as a personal attack.
- Acronyms
 - Permit acronyms with widespread cultural acceptance, e.g., "WTF" or "LMFAO".

Personal Attacks

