Consent/permission Setting: [Describe the consent/permission process including *who* will obtain it, *where* and *when* will it be obtained, and *how* much time participants will have to make a decision. Describe how the privacy of the participants will be maintained throughout the consent process.

A signed consent waiver is being requested for this study. Participants will review an informational page before completing the initial survey screener. Ample time will be allowed for

discussion or questions. Consent will be reviewed during the telephone screening by research assistants/coordinators trained in the consent process.

State whether an assessment of consent/permission materials will be conducted to assure that participants understand the information (may be warranted in studies with complicated study procedures, those that require extensive time commitments or those that expose participants to greater than minimal risk).]

We will not perform an assessment to ensure participants understand the information, however we will conduct an interactive webinar to discuss any concerns or questions.

Capacity to Consent: [Describe how the capacity to consent will be assessed for participants with limited decision-making capacity, language barriers or hearing difficulty. If a participant is incapable of providing consent, you will need to obtain consent from the participant's legal guardian (please see the IRB website for additional information).]

To be able to actively participate in the study, participants must be adults without impaired decision making ability that are able to speak and read English. The consent process will include a discussion of the participants understanding of what participating in research means including their rights as a research participant, the protocol, as well as risks and potential benefits to participating in the study. If research personnel obtaining consent believes there is a concern regarding a participant understanding participation will be discussed with the program director who will determine whether to exclude the participants on this basis.

Parent/Guardian Permission and Assent: [If enrolling children, state how many parents/guardians will provide permission, when the child's assent will be obtained and if assent will be written or oral. Provide a copy of the script to be used if oral assent will be obtained. For longitudinal studies, assent may happen at several points during the study.]

N/A

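### Does the stated burden of up to 33 hours understate participant time, because 15 minutes a day has been added up as 15 minutes a week?

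*Protocol*

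**What the plan says.** The intervention row of the Participant Time table (Protocol) reads "Intervention Pilot (24 wks)/15 min/day Virtual workshops (24 wks)/30-60/day", against 1,080-1,800 minutes. The table's grand total is 1,240-1,960 minutes, which it converts to roughly 21 to 33 hours. The section on potential harms and inconveniences carries the upper end forward: "Participants will be asked to dedicate up to 33 hours of their time over the course of 7 months".

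Other sections bear on how often each item occurs:

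- Virtual Workshops: "Participants will be asked to attend a virtual workshop weekly during the 6-month intervention". Aim 1 also describes the workshops as weekly.
- Intervention: "Participants will be encouraged to use the app daily". The same paragraph makes goal-setting and weighing weekly tasks.
- WW Beta app: the app's points budget "is how users keep track of their daily dietary intake and physical activity".

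Two activities have no line in the table. One is the short coach contacts, described as "one-on-one check-ins with their coach in addition to the virtual group workshops", of about five minutes each with no stated frequency. The other is a session mentioned under Consent/permission Setting, "we will conduct an interactive webinar to discuss any concerns or questions", with no stated length.

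**The concern.** A reader who multiplies the label out does not get the entry. Fifteen minutes a day for 24 weeks is 2,520 minutes for that item alone, which is more than the whole upper total of 1,960. Counted weekly, 15 minutes comes to about 2 minutes a day, which looks short for an app that participants are encouraged to open daily to track intake and activity. If the daily label is what was meant, the burden given to the ethics board is too low by a factor of 2.1 to 2.7.

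What would be at stake is accurate disclosure. Signed consent is to be waived, and "Participants will review an informational page before completing the initial survey screener", followed by a telephone review. People deciding whether to join should have a fair idea of the time involved. The missing check-ins and webinar add to the doubt, since the printed maximum sits only just below 33 hours.

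**Working it through.** **Inputs, all from the Participant Time table.** Screening survey 5 min; telephone screening 30 min; baseline 15 + 40 + 10 = 65 min; follow-up surveys 20 + 40 = 60 min. Fixed items: 5 + 30 + 65 + 60 = 160 min. Intervention: 24 weeks, 15 min for one item and 30-60 min for workshops.

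**Reproducing the printed entry.** The row spans 1,800 − 1,080 = 720 min. The workshop range is 60 − 30 = 30 min per session, so 720 / 30 = 24 sessions, one a week. The remainder at the low end is 1,080 − 24 × 30 = 360 min, and 360 / 24 = 15 min per week. Checking forward:

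- Row: 360 + 720 = 1,080 and 360 + 1,440 = 1,800.
- Total: 1,080 + 160 = 1,240 and 1,800 + 160 = 1,960 min, i.e. 20.7 and 32.7 h.

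This matches the table exactly.

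**Other ways of counting** (24 × 7 = 168 days; 24 × 5 = 120 days):

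| 15-min item | Workshops | Row (min) | Total (min) | Hours |
|---|---|---|---|---|
| weekly | weekly | 1,080-1,800 | 1,240-1,960 | 20.7-32.7 |
| 5 days a week | weekly | 2,520-3,240 | 2,680-3,400 | 44.7-56.7 |
| daily | weekly | 3,240-3,960 | 3,400-4,120 | 56.7-68.7 |
| weekly | daily | 5,400-10,440 | 5,560-10,600 | 92.7-176.7 |
| daily | daily | 7,560-12,600 | 7,720-12,760 | 128.7-212.7 |

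Only the first line gives the printed figures. The last two contradict the weekly schedule under Virtual Workshops. The only serious rival is the third: 168 × 15 = 2,520 min instead of 360, a difference of 2,160 min = 36 h, or 3,400 / 1,240 = 2.7 times the low end and 4,120 / 1,960 = 2.1 times the high end.

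**Weekly or daily for the 15 minutes?** For weekly: the per-day unit appears twice in this cell and is certainly wrong once; the row, the total, the conversion to hours and the inconveniences section all agree with weekly counting; and weekly goal-setting and weighing give a 15-minute weekly item something it could refer to. For daily: app use is encouraged daily. But that sentence gives a frequency and no duration, and the table row does not name the app, so tying the 15 minutes to app use is an inference (as is tying it to the weekly tasks).

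**Check-ins, on the weekly reading.** 33 h = 1,980 min, so the slack is 1,980 − 1,960 = 20 min, or four contacts of 5 min. The frequency is not given; assuming monthly to weekly (6 to 24 contacts) adds 30-120 min, and the maximum becomes 1,990-2,080 min = 33.2-34.7 h. The largest increase is 120 / 1,960 = 6%.

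**Where the figure is used.** Justification of Sample Size rests on 150 enrolled, 15% attrition, an SD of 6.0% and a one-sample t-test. The Data Analysis section and the SAP use weights, survey scores and recorded engagement. None takes participant minutes from this table as an input.

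**The case for a change.** The strongest case for acting is that the contradiction is certain and only the sponsor knows which side is wrong. Calling it a typing slip settles the workshop unit, because another section fixes the workshops as weekly. No section does the same for the 15 minutes, and the description of the app leans towards daily activity. If daily was meant, an ethics board was told about half the true burden or less. Correcting the wording would cost little.

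Much of this stands. The conflict is real, nothing in the documents excludes the daily reading, and the table omits the check-ins and the webinar. But the factor of two holds only on the less supported reading. The harm to consent is conjecture, because the information sheet is not among the documents and it is unknown whether it repeats either the label or the hours. The check-in excess rests on an assumed frequency. It is small beside a figure that the table itself calls approximate and that already assumes all 24 workshops attended at a full hour each.

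**Conclusion.** This is a clerical slip. The table's sums are sound with both items counted weekly, and the per-day unit is a demonstrable error for the workshops and probably the same error for the 15 minutes. On that reading the stated 20.7-32.7 hours stands, and unlisted check-ins would move the maximum by at most about 2 hours if held weekly. On the daily reading, which is possible but less supported, the burden would be 56.7-68.7 hours.

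Either way, no sample size, power, endpoint, analysis or conclusion of the trial depends on the figure, and the documents do not show that participants were given a wrong one. The sponsor can tidy the unit in any routine edit; the plan itself needs no change. This conclusion rests on reading the workshops as weekly, which the Protocol states, and on the absence of any design or analysis step that uses the time table.

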During the final workshop of the study (week 24), the WW coach leading the workshop will ask participants if they are interested in participating in market research focus groups sharing their thoughts and experiences about the app and other market-related questions. The participants will be told that this is not a part of this research study and that it is solely for market research for WW. The WW coach will clarify that participating in the market research focus groups does not have anything to do with this research study and it will also not affect their participation or their status as a participant in the study in any way.

Private Facebook Group – In lieu of using WW's online community that gives members an opportunity to receive motivational support from each other, participants will instead be invited to join an optional, private Facebook group. This private Facebook group will allow participants to receive motivational support from each other, but done so in a way that protects their privacy (as WW's community is open to all members). The private Facebook group will be open to study participants only. Participants will not receive any intervention content within the Facebook group. WW will be managing all aspects of the Facebook group. Members can post about their journey through photos, videos, and comments. The Facebook group will have moderator(s) from WW who ensure community standards are adhered to, but this person does not provide weight loss coaching or post any content. UConn staff may be in the Facebook group in order to use Grytics (a software program) to collect engagement data (see DSAF for Grytics information). Participants will have to "opt-in" to Grytics when they join the Facebook group so that we can download their engagement data. They will see a page about what Grytics is and what data we are collecting (their views to posts, reactions, posts, and comments in the group) and then choose to opt-in to it or not. If they do not, we cannot collect their engagement data. It is not required to do this to be enrolled in the study or to join the group.

WW Troubleshooting. If participants need technical assistance with the WW app, they will be able to email WW ([contact]) to handle any tech-based problem throughout the 6 months.

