Weight data collection – Participants will receive a WW Bluetooth scale mailed to them directly from WW. Once the participant completes the telephone screening, baseline survey, and signs the NDA, UConn staff will confirm the participants addresses in order to get them a study scale. Once that is done, UConn will send that information over to WW and WW will process and ship the scale to be directly shipped to the participant. This scale will allow participants to take their weight weekly and at assessments. Weight is logged directly from the scale to the WW scale app, which synchronizes to the WW Beta app where participants can track their weight progress. The scale app is a commercially available app called the WW Body Analysis Scale Tracker. Using a Bluetooth scale will allow for a standard weight measure for each participant with a higher level of accuracy than self-reported weight. Weight is logged directly from the scale to the participants'

WW accounts via Bluetooth. We will receive their weights from backend WW data. In the event that we are unable to get their scale to pair to the WW apps, participants can upload a screenshot of their weight through REDCap. The study team will send the participant a private survey link, and they can upload a picture of their weight displayed on the scale. From there, the study team will open the image, record the weight from the picture into a field in REDCap, and then permanently delete the image from REDCap. If it is the case that REDCap downloads the image onto the staff's computer, they will also permanently delete it as soon as it is recorded in REDCap. Study staff will help participants set-up their scale and check their BMI once the scale is working. If a participant has a BMI under 25, we exclude them from the study and provide baseline compensation. At the end of the study participants will be allowed to keep their scale.

UConn staff does not have direct access to backend data for the WW app, weight, and virtual workshops. However, WW staff will send us all relevant data throughout the study and after the 3- and 6-month assessment points.

Follow-ups:

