Follow-ups are completed at 3-months and 6-months after the start of the intervention. Participants will receive an online follow-up survey during their 13th week and 27th week after the start of the intervention. This survey will be a repeat of some of the measures assessed at baseline (indicated in the measures table below) and questions to solicit participants' feedback on the weight loss program. We will also collect weight at the 3-month and 6-month mark.

WW Memberships:

Participants will be given a free WW membership for 6-months so they can access the WW app and virtual workshops. At the end of the study, memberships will end but they will be allowed to use the publicly available WW apps and programs with purchase.

Adverse Events:

Adverse events will be formally assessed at follow-ups by asking a question in the REDCap survey. If participants gain 5% or more weight during the intervention, this will be treated as an adverse event. The participant will receive a phone call from a UConn RC and they will be asked questions about what might be going on with their weight gain. We will also re-assess Binge Eating Disorder (BED) at this time. If BED is present, we will treat it as a study-related AE. We will only re-assess BED once after the telephone screening, even if there are multiple AE's for weight gain. Participants will not be removed from the intervention if they have 5% or more weight gain.

[Describe study procedures for use of interviews or focus groups if applicable. Include details such as how long each procedure will take to complete, who will be asked to participate in these procedures and where these procedures will be conducted. Provide copies of interview and focus group questions/topic areas.]

N/A

[If the study includes *measures, survey instruments and questionnaires (including the collection of demographic data)*, identify each and, if available, provide references for the measures. Describe what they intend to measure (relate to purpose/hypothesis) and their psychometric

properties (e.g., reliability and validity). Identify any that were specifically created for the study and attach a copy for IRB review.]

Data Collected	List of Measures	Screening	Baseline	During Intervention	3m F/up	6m F/up	Method
BMI	Height	X					REDCap
	Weight	X	X	X	X	X	Scale/REDCap
Demographics	Age, gender, income, employment, marital status, race/ethnicity, household composition*	X	X				REDCap

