[Describe the conditions under which participants may be removed from the study, i.e., noncompliance with study rules, study termination, etc.]

Participants will be withdrawn from the study if: they drop from participation, do not complete all screening procedures or post inappropriate content on the social network. Participants reporting that they would like to withdraw from the study will be given the option to: 1) withdraw from all intervention-related activity and contacts, but still complete the final assessment or 2) withdraw from the study completely with no additional study contact. If a participant becomes pregnant during the study, they will be withdrawn from the intervention, but will be given the option to still complete the follow-up assessments.

Potential Harms/Risks and Inconveniences: [Describe the potential risks to participants (and secondary participants, if applicable) and *steps taken to minimize risks* for each participant population. Assess the likelihood of the risk occurring and, if it were to occur, the seriousness to the participant. Types of risks to consider include, but are not limited to: physical, psychological, social, legal, employment, and financial.]

Possible risks for being in this study includes: Injury while exercising, breach of confidential information, and discomfort completing measures. The attempt to avoid risks to participants will be addressed by: suggesting moderate intensity exercise to avoid discomfort, pain, or injury. Participants reporting discomfort will be referred to their PCP. Injuries are unlikely to occur since we screen out medical conditions that could make someone prone to injury and we only suggest moderate activity. Moderate-level physical activity is 3.0 - <6.0 METs, which includes activities such as walking briskly (2.5 to 4 mph), playing doubles tennis, or raking. We also provide

participants with information on exertion level and remind them to seek medical attention if there is pain. Tracking data will be stored electronically in REDCap, a network secure data entry program; any data on paper will be stored in a locked file cabinet; and participants will be informed that they may withdraw from the study at any time if they feel discomfort with any of the study procedures.

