Since this study is minimal risk we will not have a safety board. Data will be monitored by the data manager weekly and at the end of each assessment phase. Data from tracking forms and surveys, and engagement data received from WW will be cleaned and assessed for missingness. A full report will be generated at 6-months for PI and WW review. The report will be submitted to the IRB at the closing of the project.

Adverse events will be assessed at follow-ups UConn staff will follow an AE protocol, which will include instructions on what is considered an adverse event and what steps are needed to be taken.

Privacy/Confidentiality Part 1: [Explain how the privacy interests of participants will be maintained during the study (note that **privacy pertains to the individual not to the data**). Describe how data will be coded. Do not use the any potentially identifiable information such as initials of participants as part of the code. Explain how long data will be kept in an identifiable format and how long de-identified data will be retained. Explain how long the master key or audio or video recordings obtained, will be kept. Consider whether keeping de-identified data will be retained indefinitely and whether participants may be contacted for a follow-up study (explain procedures to retain identifiable contact data is kept.)]

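### Apart from the weight-gain rule, harms are solicited only in the week 13 and week 27 surveys, and no harm or reason question is described at withdrawal, so a harm that leads to complete withdrawal may go unrecorded

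*Protocol*

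**What the plan says.** **Solicitation.** The Protocol, Adverse Events, says: "Adverse events will be formally assessed at follow-ups by asking a question in the REDCap survey". Data Safety Monitoring repeats it: "Adverse events will be assessed at follow-ups". The Follow-ups section gives the timing: "Participants will receive an online follow-up survey during their 13th week and 27th week after the start of the intervention".

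**Second active route.** The Adverse Events section adds: "If participants gain 5% or more weight during the intervention, this will be treated as an adverse event". The response is direct contact: "The participant will receive a phone call from a UConn RC and they will be asked questions about what might be going on", together with a single re-assessment of binge eating disorder. The rule can act between surveys, because under Weight data collection "This scale will allow participants to take their weight weekly and at assessments".

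**Withdrawal.** The paragraph on removal and withdrawal, after the exclusion criteria, gives two options. One is to stop the intervention but still do the final assessment. The other is to "withdraw from the study completely with no additional study contact". A participant who becomes pregnant leaves the intervention and may choose to complete follow-ups. No harm or reason question is described for any of these.

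**Risks named.** Potential Harms/Risks and Inconveniences lists injury during exercise, breach of confidentiality and discomfort with the measures. Risk/Benefit Analysis adds psychological discomfort from the surveys or the app.

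**Other text.** Data Safety Monitoring refers to a separate adverse event protocol, which is not among the documents. The SAP contains no adverse event analysis and no denominator for one.

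**The concern.** Injury and discomfort are plausible reasons to leave a weight loss program. If the only general question about harm is in a follow-up survey, a person who leaves because of a harm and chooses no further contact is not asked about that harm. The people missed may then be those most likely to have something to report, and the count would err in a predictable direction.

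The IRB form's instruction under Data Safety Monitoring asks how adverse events will be found, assessed and reported promptly. For a harm that ends participation, the documents describe no solicited route. Because the SAP sets no denominator, the final report would also not show how many participants were never asked.

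The interpretation of the adverse event count is at stake. The weight analysis is not affected.

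**Working it through.** **1. The plan's own figures.** From Justification of Sample Size: 150 enrolled, 15% attrition, 127 completers, SD 6.0%, mean change 1.5%, two-sided alpha 0.05.
- Completers: 150 × (1 − 0.15) = 127.5, stated as 127.
- Power: noncentrality = (1.5 / 6.0) × √127 = 2.82 on 126 degrees of freedom, which gives 79.8% against the stated 80%.

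Both reproduce. The documents give no figure for adverse events, so only the counts 150 and 127 are carried forward.

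**2. Who is asked, and when.**

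| Participant | Week 13 question | Week 27 question | Asked about the harm behind leaving? |
|---|---|---|---|
| Completer | yes | yes | not applicable |
| Stops intervention, does final assessment | not stated if leaving before week 13 | yes | yes, but late |
| Withdraws completely before week 13 | no | no | no |
| Withdraws completely after week 13 | yes, if survey answered | no | no, if the harm came later |
| Silent drop-out or survey non-responder | depends on response | no | no |

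The weight-gain rule applies alongside these rows while weigh-ins continue. It identifies weight gain, not injury or distress.

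**3. Upper figure for those without a final answer.** 150 − 127 = 23, and 23 / 150 = 15.3%. This is total attrition, and the plan does not divide it. If 25%, 50% or 75% of the 23 withdrew completely (assumed shares), that would be about 6, 12 or 17 people, or 4.0%, 8.0% or 11.3% of 150.

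**4. Bounds without assumed harm rates.** Suppose all 127 completers answer and none of the 23 does. With k completers reporting a harm, the proportion in 150 lies between k / 150 and (k + 23) / 150.
- k = 0: 0% to 23 / 150 = 15.3%.
- k = 6 (6 / 127 = 4.7%): 6 / 150 = 4.0% to 29 / 150 = 19.3%.

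**5. Illustration with assumed rates** (none is in the documents), still treating all 23 as unasked. Let a be the rate in completers and w the rate in leavers. The true rate is (127a + 23w) / 150 and the share of harms missed is 23w / (127a + 23w).

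| a | w | Harms in completers | Harms in leavers | True rate | Rate among asked | Recorded / 150 | Share missed |
|---|---|---|---|---|---|---|---|
| 5% | 5% | 6.35 | 1.15 | 5.0% | 5.0% | 4.2% | 15% |
| 5% | 20% | 6.35 | 4.60 | 7.3% | 5.0% | 4.2% | 42% |
| 10% | 10% | 12.7 | 2.3 | 10.0% | 10.0% | 8.5% | 15% |
| 10% | 30% | 12.7 | 6.9 | 13.1% | 10.0% | 8.5% | 35% |

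At equal rates the rate among those asked is unbiased, although 15% of events are still lost. It is too low only when leavers have the higher rate. Dividing by 150 alone treats the unasked as harm-free, so it understates the rate even at equal rates. That is why both denominators are needed.

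**The case against.** The strongest reply has four parts.

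- **Surveys are not the only route.** A reader might infer that harms are asked about only twice. The weight-gain rule contradicts that: it acts between surveys and includes a phone call. There are also unsolicited routes. Participants can email the team, workshops and short coach check-ins run throughout, discomfort that is reported leads to referral, and the Facebook group is read by sponsor staff. This stands, and it makes loss of a harm a risk, not a certainty. It does not close the gap, because these routes depend on the participant volunteering the harm, and no text tells coaches to pass harms to the study team.
- **Few leavers are wholly unasked.** Being asked at neither survey fits complete withdrawal before week 13, and those who miss both surveys. Others may have answered once or may do the final assessment. This stands, and it is why 23 is only a ceiling.
- **The unseen adverse event protocol may cover withdrawal.** It may. The Protocol describes it as defining events and the steps to follow, and in the same place sets assessment at follow-ups.
- **The study has no safety objective.** A reader might infer that the minimal-risk classification rests on the adverse event count. It does not. The request for a waiver of signed consent justifies it in advance, and Data Safety Monitoring uses it as a premise. The aims and SAP define no safety endpoint.

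A reader might also want an extra question at week 24, when the last workshop is held. The documents do not make that case. The week 27 survey already follows the intervention, so an earlier item would shorten recall by about three weeks and add almost no newly covered exposure.

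**Conclusion.** The point holds in a limited form. Apart from the weight-gain rule, harms such as exercise injury or psychological discomfort are solicited only in the two surveys. No harm or reason question is described when someone withdraws completely. A harm that leads to such a withdrawal may go unrecorded, so the adverse event count is likely to be too low.

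The size cannot be determined from the documents. At the planned attrition, at most 23 of 150 (15.3%) lack a final answer, and the number who withdraw completely because of a harm is probably well below that. The 15% to 42% shares missed in the illustration rest on assumed rates and on all 23 being unasked. They are not estimates for this trial. The conclusion also assumes that the unseen adverse event protocol does not already put a question at withdrawal.

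This is an inexpensive improvement to harm ascertainment. It does not alter the primary result.

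**What to change.** 1. **Protocol, paragraph on removal and withdrawal.** State that the existing adverse event question, with an item on whether harm contributed to leaving, is offered in the same contact in which a participant asks to withdraw, before the no-contact option takes effect. Answering is optional.
2. **Reporting (Data Analysis and SAP).** Report adverse events with both the number of participants actually asked and the 150 enrolled, so that unasked people are visible and are not counted as harm-free.
3. **If the adverse event protocol already covers withdrawal,** replace item 1 with a cross-reference to it.

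The cost is one existing REDCap item used at one more point, plus a short amendment. Withdrawal contacts become slightly longer and some participants will decline to answer. No extra staff or visits are needed, and no clinical rule changes. The question will not reach silent drop-outs or survey non-responders; for them, the number-asked denominator is the only safeguard.
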